5.2 Study outcome measures

The following outcomes will be measured at baseline and at 12-months post-referral as a part of the observational study, unless otherwise stated:

- Child-related outcomes (all completed by family carers)
 - Child BtC measure
 - Behaviour Problems Inventory Short Form (BPI-S) (Rojahn et al., 2012)
 - Child physical health measures
 - Children's sleep habit questionnaire (CSHQ) (Owens et al., 2000)
 - Non-communicating children's pain checklist – revised (NCCPC-R) (Breau et al., 2004)
 - Child mental health measure
 - Strengths and Difficulties Questionnaire (SDQ) (Goodman, 1997)
 - Child quality of life measures
 - EQ-5D-Y Health Questionnaire (Wille et al., 2011)

- **EITHER** Paediatric Quality of Life Inventory (PedsQL) infant scales (*only for children aged 0-24 months*) (Varni et al., 2011) **OR**
- Paediatric Quality of Life Inventory (PedsQL) Generic Core Scales (*only for children aged 2 years+*) (Varni et al., 2001)
- Child skills measure
 - GO4KIDDS (Perry et al., 2015)
- Child services received measure
 - Client service receipt inventory (CSRI) (Beecham & Knapp, 1992)
- Family-carer-related outcomes (all completed by family carers)
 - Family carer quality of life measure
 - EQ-5D-5L Health Questionnaire (van Hout et al., 2012)
 - Family carer wellbeing measure
 - Warwick Edinburgh Mental Wellbeing Scale (WEMWBS) (Tennant et al., 2006)
 - Family carer services received measure
 - Client service receipt inventory (CSRI) (Beecham & Knapp, 1992)
 - Family carer experience/satisfaction with service (at 12-months only)
 - Experience of service questionnaire (ESQ) satisfaction with care items (Brown et al., 2014)
- Service-level outcomes (at 12-months only) (completed by services)
 - 'Reach' to population
 - Timings of service delivery (e.g., mean time to starting support from referral, and length of time to discharge)
 - Service take-up
 - Costs at service level
- Other-stakeholder-related outcomes (at 12-months only) (completed by external stakeholders)
 - Satisfaction of external stakeholders (e.g., referrer, health, social-care, or education professionals) brief measure (*Developed for the purposes of this study*)

14 Study design and data collection methods

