13.1 Sample size

Following Stage 1, we identified 5 different service models. On that basis, 15 examples of services in total will be included at Stage 2 – based on sample size calculations. To detect a standardised effect

size of 0.4 in a one-way ANOVA, with 90% power, a two-sided alpha of 0.05, and assuming five service model types identified in Stage 1, a total sample size of 120 children is required. Inflating this sample size for clustering of children within services, assuming an average number of 13 children recruited from each setting and an intra-cluster correlation coefficient (ICC) of 0.05, the required sample size increases to 195 children from 15 settings. This sample size does not currently account for loss to follow up, so we will allow up to 20% by extending our sample size to N=244 (recruiting approximately 15-16 individuals per service for 15 services). This ICC is likely conservative given the subjective nature of the outcome measures (Adams et al., 2004). In our statistical analysis, we will enhance power and precision by adjusting for individual and cluster level characteristics, including service type (which is by definition a cluster level characteristic) and corresponding baseline measures of the outcome variable.

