It is inevitable that the referral of children to different service types will be a non-random process. Therefore, a crude comparison of outcomes of children in different service types will be prone to selection bias. To minimise this, the research team and stakeholders will construct a Directed Acyclic Graph (DAG) prior to data collection in Stage 2, which will outline our core assumptions around the causal pathways between service model (exposure) and child outcomes (Williams et al., 2018). This DAG will be used to identify key quantitative data to collect (e.g., confounders, mediators, and moderators) and will be used as an aid for modelling the relationship between service model and child outcomes. The final statistical models will depend on the DAG, but will broadly be a two-level linear regression model (children nested within services), with the child outcome measure at 12-months as the outcome, service model included as a fixed effect, and the corresponding child outcome collected at baseline also included as a covariate. Results will be reported as adjusted mean differences, 95% confidence intervals, and p-values. Mediation analyses will use the bootstrapped procedure as this method has no distributional assumptions on the indirect effect and is generally more robust (Bollen & Stine, 1990).

A detailed statistical analysis plan will be written and agreed by the study management team prior to any analysis taking place. A missing data strategy will be a part of the SAP. This is most likely to include an exploration of any setting/child determinants of missing outcome data (to infer likely missing mechanisms), and an analysis that is valid under a Missing At Random assumption (e.g. using maximum likelihood methods or multiple imputation).

When fitting models to describe the relationship between our service types and our outcome/s, we will adjust for confounding using multinomial propensity score weighting, as this approach tends to preserve the majority of a study sample and therefore maximises precision of estimates. When specifying our propensity score model, we will include outcome risk factors (informed by the DAG which defines the minimally required adjustment set) and exclude strong predictors of service model inclusion that are not associated with outcome. Following this, we will inspect the distribution of

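### Stage 2 is sized on one five-group joint test of an unnamed outcome, but plans mean differences with p-values on unranked outcomes, with no joint test, contrast list or multiplicity rule

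*Protocol*

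**What the plan says.** All references are to the Stage 2 part of the Protocol unless stated.

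- **Sizing (13.1 Sample size).** "Following Stage 1, we identified 5 different service models". The target is given in standardised form as "size of 0.4 in a one-way ANOVA, with 90% power, a two-sided alpha of 0.05, and assuming five service model types identified in Stage 1", from which "a total sample size of 120 children is required". Clustering (13 children per service, ICC 0.05) raises this to 195 children in 15 services, and 20% loss to follow-up raises it to 244. The outcome to which 0.4 applies is not named.
- **Outcomes (5.2 Study outcome measures).** The list opens: "The following outcomes will be measured at baseline and at 12-months post-referral as a part of the observational study, unless otherwise stated". It has seven scored child scales (BPI-S, CSHQ, NCCPC-R, SDQ, EQ-5D-Y, PedsQL, GO4KIDDS) and three scored carer scales (EQ-5D-5L, WEMWBS and, at 12 months only, ESQ). None is ranked primary. The synopsis gives a primary objective but no primary outcome.
- **Analysis (14 Analysis, Statistical Analysis).** The model is a two-level linear regression of the 12-month child outcome on service model (fixed effect) and the baseline score. "Results will be reported as adjusted mean differences, 95% confidence intervals, and p-values". No joint test, contrast list, reference model or multiplicity rule follows.
- **Deferred detail.** Section 14 promises a Stage 2 SAP before any analysis and says that it will contain a missing-data strategy. It does not commit that SAP to a primary outcome or a multiplicity rule. The SAP supplied covers only the Stage 1 latent class analysis.

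**The concern.** A mean difference is a contrast between two models. With a five-level factor, the single question answered by the sample-size test (do the models differ at all?) is therefore not something the analysis section undertakes to report. What it does undertake to report was not sized, and nothing limits how many such results there are.

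The stated objectives include informing commissioning. Without a primary outcome or a decision rule, one isolated small p-value for one model on one scale could be read as evidence that the model is better. Conversely, a non-significant contrast could be read as equivalence when moderate differences had little chance of being detected.

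**Working it through.** **1. The plan's own sample size.** Inputs from 13.1: five groups, effect 0.4, 90% power, alpha 0.05. Reading 0.4 as Cohen's f, the noncentrality is N × f² with 4 and N − 5 df.

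- At alpha 0.05, 90% power needs N = 102 (105 in equal groups); N = 120 gives 94.8%.
- If alpha is halved to 0.025, which is one way to read two-sided for an F test, N = 117 is needed. In equal groups that is 120 (power 91.0%; 115 gives 89.4%). This reproduces 120.
- Design effect 1 + (13 − 1) × 0.05 = 1.6; 120 × 1.6 = 192, rounded up to 15 × 13 = 195; 195 / 0.8 = 243.75, so 244.
- If 0.4 meant a 0.4 SD gap between the extreme models, about 776 (equally spaced means) to 968 (two extreme models) children would be needed before clustering. So 120 fits only f = 0.4.

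**2. Number of tests if all pairs are reported.** Five models give 5 × 4 / 2 = 10 pairs. Seven child scales give 70 tests and 70 × 0.05 = 3.5 expected false positives when no model differs. Ten scales give 100 tests and 5 expected. These expectations do not depend on correlation.

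**3. Chance of at least one false positive, no true differences.** Pairs share groups and outcomes are correlated, so this was simulated. Outcome correlation is not in the documents and was varied from 0 to 0.9. The 10 df are 15 services minus 5 models.

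| Tests reported | Correlation 0 | Correlation 0.9 |
|---|---|---|
| 7 scales, all pairs, 10 df | 86% | 47% |
| 10 scales, all pairs, 10 df | 94% | 50% |
| 10 scales, all pairs, large-sample | 97% | 55% |
| 10 scales, four contrasts with a reference model, large-sample | 82% | 35% |
| 10 scales, one joint test each, large-sample | 40% | 13% |

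Simulation error moves these by about a point. The last row shows that joint tests alone do not settle the matter while ten outcomes rank equally.

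**4. Power of a pairwise contrast.** Section 16 (Selection of Services and Participants) gives three services per model, so 3 × 13 = 39 analysed children per model.

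- SE = √(2 × 1.6 / 39) = 0.286 SD. For 0.4 SD the noncentrality is 0.4 / 0.286 = 1.40. Against the two-sided 5% point of t with 10 df (2.228), power is 24%. The difference detectable with 90% power is 1.03 SD.
- Baseline adjustment is planned but not quantified. Assuming a baseline correlation r of 0.5 to 0.7, with SE multiplied by √(1 − r²) and the ICC unchanged, power at 0.4 SD is 31% to 42% and the 90% detectable difference is 0.89 to 0.74 SD.

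**5. What f = 0.4 implies for contrasts.** The largest pairwise difference depends on the pattern of means:

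- two models against the other three: 0.4 × 5 / √6 = 0.82 SD;
- equally spaced: 0.4 × √8 = 1.13 SD;
- two extreme models, the rest central: 0.4 × √10 = 1.26 SD.

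Unadjusted power for differences from 0.82 to 1.26 SD is 81% to 99% with large-sample critical values. With 10 df it is 73% (noncentrality 0.8165 / 0.2864 = 2.85) to 98%. Bonferroni over ten pairs lowers the large-sample figures to 52% to 95%.

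**The case against.** **All pairs is an inference.** Section 14 says only adjusted mean differences. Four contrasts with a reference model would fit the words, and a joint test is not excluded. This stands, and the false-positive figures are therefore conditional. Even so, the reference-model reading gives 35% to 82% for ten scales, and no text restricts the contrasts.

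**The stated model is for child outcomes.** This also stands. The model covers seven scales, and ESQ has no baseline value to enter it. A reader might infer that the plan commits to 100 p-values; it does not. The child-scale count is 70, and only if all pairs are reported.

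**False positives are not near certain.** A reader might infer this from 1 − 0.95^100 = 99.4%. That requires 100 independent tests, which is impossible when pairs share groups, and no true difference anywhere.

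**The 24% mixes two effect scales.** The design target is f = 0.4, not a 0.4 SD gap between two models. A reader might infer that the contrasts are not powered at all, or that the design misses its own target. Step 5 shows otherwise for the largest contrasts. The shortfall concerns moderate differences. Baseline adjustment would raise power; propensity weighting would generally lower it.

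**A Stage 2 SAP is promised.** Contrasts and multiplicity are ordinary SAP content, and their absence here does not show that no rule will exist. But the commitment in section 14 does not mention them, the document was not supplied, and it need only be agreed before analysis. The primary outcome belongs in the protocol in any case.

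**Conclusion.** The concern holds in this limited form. Stage 2 is sized on one joint test of an unnamed outcome. Its stated results are mean differences with p-values on unranked outcomes, with no joint test, contrast list or multiplicity rule. This is more than missing detail: followed as written, the plan does not report the hypothesis it was sized for and has no rule for declaring that models differ.

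The false-positive range (47% to 86% for seven scales, 50% to 94% for ten) assumes that all pairs are reported and that no model differs on anything; it is lower for contrasts with a reference model. The power figures assume 39 analysed children per model, the protocol's ICC, 10 between-service df and no weighting. Outcome and baseline correlations are assumed ranges.

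The documents support saying that false positives are likely under that reading and that moderate pairwise differences are poorly powered. They do not support saying that error is certain or that no contrast has adequate power. The change should be made.

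**What to change.** In the protocol and the Stage 2 SAP, before outcome data are analysed:

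1. Name one primary outcome. BPI-S at 12 months is the natural candidate, as the listed measure of behaviours that challenge; the team may justify another.
2. Make the 4-df joint test of service model on that outcome the primary test, so that it matches the sample size.
3. After that test, report pairwise contrasts on the primary outcome with a stated adjustment, such as Tukey or Holm.
4. Label all other outcomes secondary or exploratory and report estimates with confidence intervals. Whether to print their p-values as well is a matter of preference once they are so labelled.
5. State the detectable pairwise difference at 39 analysed children per model (about 1.03 SD for 90% power, unadjusted for baseline and before multiplicity adjustment), and state that 0.4 is Cohen's f.

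The cost is about a paragraph in each document, with no further children, services or data. The downside is that secondary scales and individual contrasts carry less inferential weight, and adjustment lowers pairwise power further.

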6.2 Risk assessment

This is a low-risk study. The research is purely observational, and no interventions will be implemented outside of the treatment as usual within services. Involvement in the study is entirely voluntary, and informed consent will be obtained prior to any data collection with participants. Participants will be asked questions about their/their child's wellbeing, mental health, health, quality of life, and experience of the service using measures that are routinely used in research with children and young people with learning disabilities.

We will complete a formal risk assessment before the study commences.

15 Site and Investigator selection

Each service, and each co-production case study will be a separate site, and a PI will be identified within each site. Identification of services is described in detail in Section 8 below. Identification of Co-Production Case Studies will be undertaken with the involvement of the family carer advisory group, professionals advisory group, and the SMG.

The study will be carried out at University of Warwick, under the supervision of the Chief Investigator ([name]). Fully trained Research Fellows and Research Assistants at the University of Warwick will be responsible for recruitment and all data collection. A Site Delegation Log and Roles and Responsibilities document will be completed and full contact details will be recorded for all Sites. A Site File, containing all relevant study documents will be prepared at the University of Warwick.

Once all study documentation is in place and a Site Initiation Visit has been completed, recruitment of services and participants into the study will begin.

Occasionally during the course of the study, amendments may be made to the study documentation, required approvals obtained, and the latest approved versions will be added to the Site File.

16 Selection of Services and Participants

All eligible services from Stage 1 of the MELD study will be considered (N=161), and sampling of services will be according to a systematic sampling process to select 15 Sites from the approximately 161 services included in Stage 1 (3 services per Class).

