propensity scores for distributional overlap. We will consider trimming of extreme weights (i.e., probabilities close to zero or one), but will investigate the extent to which trimming limits the generalisability of our findings. We will then estimate the “average treatment effect in the whole population” (i.e., the effect of service model on outcomes in all referred children) by fitting models with inverse probability of treatment weights and robust sandwich-type estimators for variance estimation.

Economic Analysis

An economic evaluation of the selected service models will be incorporated into Work Package 2.1; data gathered about co-production activities will be incorporated into Work Package 2.2. This will take the form of a cost-consequence analysis, which will involve the identification, measurement, and valuation of all costs and consequences of the selected service models and co-production activities as well as the presentation of data in a disaggregated tabular format for comparison. The cost consequence analysis will be carried out from a public sector perspective. Data related to the direct costs of each service model will be informed by primary research (using a standard proforma) that will account for the cost of service delivery, monitoring, follow-up, and associated administrative activities. Individual-level data on broader resource consequences and associated economic costs will be informed by CSRs completed by each child’s primary parental caregiver at baseline and at a 12-month follow-up. In addition, data on each measure included in the outcomes package will be collected and reported separately. Mean costs and outcomes for each service model will be estimated together with appropriate measures of uncertainty such as standard errors and confidence intervals. To handle potential selection biases within the economic evaluation, we will apply propensity score matching methods to balance the characteristics of individuals in each comparator group and to ensure consistency with the statistical analysis, before conducting a cost-consequences analysis of the alternative service model types. Our analytical strategy will be informed by recent guidance on the conduct of health economic analyses using individual patient level observational data (Kreif et al., 2013).

A detailed Health Economics Analysis Plan (HEAP) will be written and approved prior to the completion of Stage 2 data collection.

Qualitative Analysis

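### Stage 2 plans sandwich variances on 15 services (3 per model) without stating a small-sample correction, clustering level or reference distribution; with large-sample defaults, error rates would be far above nominal

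*Protocol*

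**What the plan says.** All references are to the Stage 2 protocol (Appendix 2 of the protocol document) unless noted.

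- **Variance.** Section 14, Statistical Analysis, plans models with "inverse probability of treatment weights and robust sandwich-type estimators for variance estimation".
- **Model and reporting.** The same section says the analysis "will broadly be a two-level linear regression model (children nested within services"), with service model as a fixed effect and the baseline value of the outcome as a covariate. It adds: "Results will be reported as adjusted mean differences, 95% confidence intervals, and p-values".
- **Clusters.** The section on selection of services and participants will "select 15 Sites from the approximately 161 services included in Stage 1 (3 services per Class").
- **Sample size (13.1).** The basis is an effect "size of 0.4 in a one-way ANOVA", "with 90% power, a two-sided alpha of 0.05", "assuming five service model types identified in Stage 1". This gives 120 children, then 195 after allowing for 13 children per service and an ICC of 0.05, then 244 after 20% loss. The section itself recognises service type as a cluster-level characteristic.
- **Not stated.** No small-sample correction, clustering level for the sandwich, or reference distribution for intervals and tests is given. Section 14 leaves detail to a Stage 2 SAP. The SAP supplied covers Stage 1 only, and its section 4 says Stage 2 will have its own.

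**The concern.** A sandwich variance is justified by a large number of independent units. Here the exposure is fixed at service level, so the independent units for comparing models are the services: 15 in all and three behind each model mean. There are 15 − 5 = 10 between-service degrees of freedom, before any service-level covariate is fitted.

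Two things go wrong if a service-clustered sandwich is used with large-sample defaults. Residuals taken around a mean of only three services are too small, so the variance is biased down. Normal or chi-square critical values also ignore how poorly that variance is estimated. If the sandwich is instead computed on children, the between-service variation that section 13.1 allows for drops out of the standard error.

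Stage 2 exists to compare outcomes across models and inform commissioning, on many outcome measures. Intervals that are too narrow would show differences between models that reflect only which three services were chosen.

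**Working it through.** **1. The plan's own figures.** Section 13.1 does not say what the effect size of 0.4 is. I read it as Cohen's f because the test is a one-way ANOVA. For five groups, alpha 0.05 and 90% power, the noncentral F gives 102 children (105 if balanced), not 120. At 120 the power is 94.8%, so the difference is on the safe side. The later steps reproduce:

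- Design effect: 1 + (13 − 1) × 0.05 = 1.6.
- 120 × 1.6 = 192, rounded up to 15 × 13 = 195.
- 195 / 0.8 = 243.75, i.e. 244.

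The documents give no interval width or error rate for the sandwich analysis.

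**2. Difference between two models, sandwich clustered on service.** Take equal cluster sizes. The uncorrected variance (CR0) of a model mean is Σ(service mean − model mean)² / 9 over three services. Its expectation is 2/3 of the true variance, so the standard error is about √(2/3) = 0.82 of its correct size. For two models, the correctly scaled statistic follows t on 2 + 2 = 4 df.

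- *CR0 with normal critical value:* P(|t₄| > 1.96 × 0.816) = P(|t₄| > 1.60) = 18.5%.
- *Usual correction (CR1) with 14 df:* the standard error ratio is √[(2/3) × (15/14) × (194/190)] = 0.854. P(|t₄| > 2.145 × 0.854) = P(|t₄| > 1.83) = 14.1%.

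The calculation therefore gives coverage of about 81.5% to 86%. Simulated false-positive rates for these two choices run up to about 19% and from about 13%, in line with this. The ICC cancels because both the difference and its standard error depend only on service means.

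**3. Overall test and the alternatives.** Simulation under no difference: 5 models × 3 services × 13 children, nominal 5%, ICC 0.05.

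| Method | Overall | Two models |
|---|---|---|
| Clustered, uncorrected, chi-square / z | 48% | 19% |
| Clustered, CR1, F(4,14) / t(14) | 34% | 14% |
| Not clustered on service, chi-square / z | 25% | 14% |
| Service means, F(4,10) / t(10) | 5% | 5% |
| CR2 with t(4) | – | 5% |

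A separate set of runs added a baseline covariate, with and without variable weights, at ICC 0.01, 0.05 and 0.10. The overall error for the clustered sandwich was 44–49% with chi-square and 34–39% with F(4,14), with no trend in ICC.

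The unclustered sandwich does depend on ICC. Without covariates its overall error is about 10%, 25% and 41% at 0.01, 0.05 and 0.10. With the covariate it is 9–10%, 22% and 37–40%.

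**4. Two-level model with model-based standard errors, for comparison.** At ICC 0.05 with z or chi-square, REML gives 6.6% for two models and 9% overall. Maximum likelihood gives 10% and 17%.

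**5. Power on the correct degrees of freedom.** With 195 analysed, f = 0.4 and ICC 0.05, the noncentrality is 195 × 0.16 / 1.6 = 19.5. Power is 81% on F(4,10), against 95% on F(4,190). On F(4,10) it is 93% at ICC 0.01 and 66% at ICC 0.10. None of these includes the gain from baseline adjustment or the loss from weighting.

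**The case against.** The strongest reply is that the protocol does not say the sandwich is uncorrected. A reader might infer that the plan commits to the ordinary estimator, and hence that its intervals will be far too narrow. The text does not support that: a sandwich-type estimator is a family that includes CR2. Detail is deferred to a Stage 2 SAP that is not among the documents, which is where a degrees-of-freedom method would normally appear. This stands, and the point has to be conditional.

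Four further replies have some weight.

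- *The model is two-level.* A reader might infer a child-level sandwich, because that is often what follows propensity weighting. The nested model and the inflation for clustering point the other way. The documents settle neither reading, and the unclustered figures depend on the ICC, which section 13.1 regards as probably conservative.
- *The largest figure needs three choices together:* an uncorrected variance, chi-square critical values and an overall test. The reporting sentence promises only mean differences, intervals and p-values; an overall test is implied by the ANOVA sample size. The pairwise result of 14–19% does not need it.
- *Model-based REML inference would be much closer to nominal.* True, but section 14 names the sandwich for the weighted models, and Wald tests without a degrees-of-freedom method remain above 5% overall at ICC 0.05.
- *The bootstrapped mediation analysis.* A reader might infer that it must be called exploratory. Nothing in the documents requires that; only its resampling unit is at issue here.

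The deferral does not remove the point. The protocol has already chosen the type of estimator. A Stage 2 SAP that repeats the sentence and accepts common software defaults would carry the error forward.

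**Conclusion.** The concern holds in conditional form. The plan names sandwich variances for a cluster-level exposure with three services per model and leaves open the choices that decide whether the inference is valid. Under the usual large-sample defaults with clustering on service, 95% intervals for two models cover about 81–86%, and the overall 5% test rejects about 34–48% of the time under no difference. A smaller ICC is no defence, since this holds from 0.01 to 0.10. Without clustering on service, the overall error is about 10%, 25% or 41% at ICC 0.01, 0.05 or 0.10.

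These figures assume normal outcomes and equal service sizes. The weights that were tried were unrelated to outcome, and estimation of the propensity score was not simulated. The power figures read 0.4 as Cohen's f. The documents do not support saying that the planned intervals are wrong as written. They support saying that nothing in the plan prevents it.

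**What to change.** In section 14 of the Stage 2 protocol and in the Stage 2 SAP, before analysis:

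1. State that the variance of the weighted models is clustered on service with a small-sample method. Either use CR2 (Bell–McCaffrey) with Satterthwaite df, or a weighted service-level analysis on F(4,10) and t(10), with df reduced for any service-level covariate.
2. For any unweighted two-level model, use REML with Kenward–Roger df.
3. In any bootstrap, including mediation, resample services.
4. Restate the power.

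The two options in item 1 are not interchangeable. CR2 has about 4 df for a contrast of two models, so its critical value is 2.78 against 2.23 on 10 df, and its intervals are about 25% wider (2.78 / 2.23 = 1.25). The 10-df analysis assumes equal between-service variance across models, and section 13.1 plans cluster-level adjustment, which would use some of those df.

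The cost is wording, standard software and wider intervals. The planned 90% also has to be replaced: with 195 analysed, f = 0.4 and ICC 0.05, overall power on F(4,10) is about 81% before baseline adjustment or weighting loss.
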